6. QUALITY CONTROL	
A. Data Collection	37
B. Reports and Site Visits	37

7.	TRIAL ORGANIZATION	
	A. Clinical Centers (CCs)	37
	B. Clinical Coordinating Center (CCC)	38
	C. NHLBI Project Office	38-39
	D. Steering Committee	39
	E. Steering Committee Subcommittees	39-40
	F. Protocol Review Committee and Data Safety Monitoring Board	40
	G. Clinical Coordinating Center (CCC) subcontracts	40-41
	H. Publications and Presentations Policy Objectives	41
	I. Ancillary Studies	41-42
8.	REFERENCES	43-49
	TABLE 1 Schedule of Activities	50
	TABLE 2 The Three Groups Of Standard Care, Staff Assistance, Staff Counseling	51
	FIGURE 1: Protocol for Maximal Graded Exercise Test (SV1)	52
	APPENDIX A - ACT Physician "Letter of Understanding"	A-1
	APPENDIX B - Organizational Structure and Participating Centers	B-1 - B-2
	APPENDIX C - Model Informed Consents	C-1 - C-5
	APPENDIX D - Publications and Presentations Policies	D-1 - D-11

SUMMARY OF ACTIVITY COUNSELING TRIAL

The Activity Counseling Trial (ACT) is a randomized clinical trial to evaluate the efficacy of two primary care, practice-based physical activity behavioral interventions. Approximately 810 sedentary men and women 35-75 years of age will be enrolled in the study, including substantial minority representation. Each participant will receive two years of intervention and follow-up. Participants will be enrolled over a period of 15 months or less.

The three study groups, simultaneously implemented at three clinical centers (located in California, Texas, and Tennessee) will consist of the same initial physician assessment and advice. Participants assigned to the two intervention groups also will receive varying levels of practice-based intervention. The interventions are based on behavior change theory, but they differ in the amount of resources required for implementation. The three study groups are as follows:

GROUP A: STANDARD CARE

This group will provide physician assessment and advice and written materials. It will not offer behavioral counseling.

GROUP B: STAFF ASSISTANCE

This intervention is a subset of the Staff-Counseling Intervention and requires fewer resources and less staff time. A guiding principle in developing this intervention was for it to be feasible for delivery in a wide variety of primary care settings without requiring extensive staff support. The intervention employs brief in-person counseling, video, interactive mail, referral to community resources, and occasional telephone contact.

GROUP C: STAFF COUNSELING

This intervention is designed to be an optimal intervention that could be delivered in a primary care setting. It requires substantial staff involvement and employs on-site interpersonal counseling, regular telephone follow-up counseling, in-clinic follow-up counseling, written and visual materials, interactive mail, onsite classes, and referral to community resources.

There will be two primary study outcomes: (1) maximal oxygen uptake (VO_{2max}) ($L \cdot min^{-1}$) measured by a maximal treadmill test using a standardized protocol, and (2) kilocalories expended in physical activity ($kcal \cdot kg^{-1} \cdot min^{-1}$) measured by a standardized and validated self-report instrument, the seven-day physical activity recall. To determine the relative efficacy of the interventions, comparison between groups for mean changes in the outcome measures will be performed. All analyses will be done separately for men and women. Change from baseline to two years will be the primary outcome analysis. Short-term effects will be examined by change from baseline to six months. Secondary outcomes related to cardiovascular disease risk include plasma lipids/lipoproteins (e.g., triglycerides and HDL), blood pressure, body composition (body mass index, skinfolds, waist-to-hip ratio), plasma insulin, fibrinogen, dietary intake, smoking, heart rate variability, cost-effectiveness, and psychosocial factors. Subgroup analyses also will be conducted.

1. INTRODUCTION

1.A. Background and Significance

Sedentary habits and low levels of cardiorespiratory fitness are important risk factors for cardiovascular disease (Blair, 1989,1992,1993,1994; Blair, McCloy 1993; Ekelund, 1988; Morris, 1990; Kaplan, 1987; Shaper, 1991), non-insulin-dependent diabetes (Helmrick, 1991; Manson, 1992; Gudat, 1994), some cancers (Lee, 1994), and functional limitations (Wagner, 1992; Buchner, 1992). All-cause death rates are approximately doubled in sedentary as compared with active individuals (Blair, 1994; Paffenbarger, 1986), and range up to three times higher in unfit men and women when compared with their physically fit peers (Blair, 1989; Blair, 1994). The relative risk of cardiovascular disease mortality is as high as 7.0 or 8.0 in the least physically fit quartile or quintile when compared with the most fit quartile or quintile of men and women (Blair, 1989; Blair, 1994).

Less than one quarter of adults are active at the level recommended for health benefits in objective 1.3 of Healthy People 2000 (DHHS, 1991), and approximately 25% of adult Americans are essentially totally sedentary (CDC, 1990). The strength of the association between inactivity and cardiovascular disease deaths, and the high prevalence of sedentary lifestyles lead to a high population attributable risk. Population attributable risk estimates for sedentary habits for coronary heart disease (CHD) death range from 29% to 40% across the several states that participate in the Behavioral Risk Factor Surveillance System (CDC, 1990). A report from the U.S. Centers for Disease Control and Prevention (Hahn, 1990) presented estimates of excess deaths in the U.S. from nine chronic diseases (based on 1986 national mortality data). The number of excess deaths for the diseases that could be attributed to several risk factors also was estimated. Smoking had the greatest impact, and was estimated to have caused 361,911 excess deaths in 1986. High levels of cholesterol or blood pressure, obesity, and sedentary habits were comparable in estimated number of excess deaths, with about 250,000 deaths attributed to each of these risk factors.

Increases in physical activity confer several important health benefits, such as reductions in elevated blood pressure (Duncan, 1985; ACSM, 1993), improvements in the lipoprotein profile (Stefanick, 1994), increases in cardiorespiratory fitness (Blomqvist, 1983; Duncan, 1991), improvements in carbohydrate metabolism (King, 1987; Rodnick, 1987; Sato, 1986), and reductions in body fat (Blair, 1993; MacKeen, 1985; MacKeen 1983). Physical activity and cardiorespiratory fitness provide protection against cardiovascular disease mortality in men and women who are at high risk based on the other major risk factors of hypertension, elevated cholesterol, and cigarette smoking (Blair, 1989; Blair, 1993; Shaper, 1991). Recent prospective population studies show a reduction in cardiovascular and all-cause mortality in initially sedentary men who become physically active (Paffenbarger, 1993; Blair, 1993). The reduction in mortality risk in these two studies with increases in physical activity is substantial (on the order of a 50% reduction) and is comparable to risk reductions associated with other beneficial changes, including stopping smoking, losing weight, and lowering blood pressure and cholesterol.

The convincing evidence for health benefits of a physically active way of life in conjunction with the high prevalence of inactivity in the U.S. population has led various groups to identify physical inactivity as a target for interventions designed to improve the public's health. Recent statements on physical activity include reports by the American Heart Association (Fletcher, 1992) and the U.S. Surgeon General (DHHS, 1991). A recent recommendation from the Centers for Disease Control and Prevention and the American College of Sports Medicine (CDC-ACSM) is that every American adult should accumulate 30 minutes or more of moderate intensity physical activity on most,

preferably all, days of the week (Pate, 1995). Moderate-intensity physical activity is defined as 3-5 Metabolic Equivalents (METs), the equivalent of brisk walking at 3-4 miles per hour for most healthy adults. Increases in physical activity can lead to increases in cardiorespiratory endurance, the component of physical fitness that is important for reducing cardiovascular disease risk (Blair, 89; Blair 93; Ekelund, 88).

Patterns of physical activity vary with demographic characteristics (Pate, 1995). Men are more likely than women to engage in physical activity (Dishman, 1991) and the total amount of time spent engaging in physical activity declines with age (Caspersen, 1992). African-Americans and other ethnic minority populations are somewhat less active than White Americans and this disparity is more pronounced for women (Caspersen, 1992). People of higher socioeconomic status participate in more leisure time physical activity than those of lower socioeconomic status. Some of the racial and ethnic differences in physical activity may reflect differences in socioeconomic status.

Characteristics of the individual and of the type of activity are related to participation in physical activity. Lack of time and concerns about injury are common reasons people do not participate in regular physical activity (Martin, 1982). Persons who are obese are often inactive (Bouchard, 1993). An intention to exercise and awareness of the benefits of exercise are weakly related to participation in physical activity; on the other hand, confidence in one's ability to be physically active and to overcome barriers to inactivity and enjoyment of activity are strongly related to participation (Sallis, 1989). Low to moderate intensity activities are more likely to be continued than high intensity activities. Self-regulatory skills, social support, and conducive environments are also associated with increased physical activity.

Physicians and other health care providers have been identified as important avenues for reaching sedentary individuals and encouraging increases in their physical activity. Healthy People 2000 includes an objective on physician counseling for physical activity (DHHS, 1991), and the U.S. Preventive Services Task Force recommends counseling by physicians for all sedentary patients (Harris, 1989). Despite the recommendations, data show that relatively few primary care physicians routinely inquire about their patients' exercise habits and attempt to intervene in the sedentary (Williford, 1992; Taylor, 1983). Although physicians express an interest in physical activity counseling, they often lack the time to enter into discussions about exercise with their patients and may not feel they have the skills to provide physical activity counseling.

Despite difficulties and barriers, physical activity intervention in primary care practices offers promise. Most middle-aged and older adults who are at high risk for premature mortality see a physician at least once a year (Williford, 1992; Taylor, 1983; Kelly, 1992; Valente, 1982). Physicians have high credibility regarding health recommendations, and surveys show that patients are inclined to act on their doctors' advice (Williford, 1992; Taylor, 1983; Kelly, 1992; Valente, 1982). Physical activity interventions in the community and other sites, such as work sites, need to be supported, but intervention in primary care practices should be viewed as an important part of the overall public health effort to get more adults to be more active more of the time.

National recommendations advise health-care professionals to intervene to increase physical activity levels of their patients, but strategies of how to intervene have yet to be tested thoroughly in studies of interventions delivered in health-care settings. Physical activity intervention studies demonstrate increases in activity in adult men and women (King, 1991; Sedgwick, 1980; Sedgwick, 1988; MacKeen, 1985; MacKeen, 1983). A few controlled studies have tested intervention approaches for

long-term change in physical activity, which is important for risk reduction, and have achieved success in promoting long-term increases in physical activity (Kriska, 1986; Juneau, 1987; King 1991). No studies, however, have tested intervention approaches delivered in primary health-care settings directly to patients for primary prevention.

This clinical trial will develop and test interventions to increase and maintain physical activity and cardiorespiratory fitness specifically in health-care settings for primary-care patients. Thus, the goal of ACT is to develop and test the efficacy of physical activity interventions delivered in a primary-care setting. This trial will demonstrate whether interventions delivered in a primary care clinical setting can be successful in long-term increases in physical activity and cardiorespiratory endurance. The ultimate goal is to develop successful strategies that can be implemented in medical practices, with the end result of an increase in physical activity by adults in the U.S. and an improvement in public health.

1.B. Objectives of the Activity Counseling Trial (ACT)

The goal of ACT is to develop and evaluate two intervention models of primary-care, practice-based activity counseling to determine their effectiveness in increasing and maintaining physical activity and cardiorespiratory endurance in previously sedentary participants from primary-care practices.

1. Primary Objectives

Since the goal of the two interventions is to increase physical activity, quantification of the amount of energy expended in physical activity is a primary outcome of ACT. The 7-day Physical Activity Recall (PAR) remains the most accepted method for estimating kilocalories expended through physical activity in population-based studies. Self-report measures of behaviors such as physical activity, however, may be imprecise and self-report changes can be exaggerated. Cardiorespiratory endurance is an important health-related component of fitness that reduces cardiovascular disease risk and is increased by physical activity. Maximal oxygen consumption (VO_{2max}) does not measure energy expenditure or physical activity, *per se*, but is an accurate and reliable measure of cardiorespiratory endurance and usually increases with increased physical activity at the level targeted for this study. Although physical activity is related to cardiorespiratory endurance, increases in some types of physical activity may result in greater expenditure of kilocalories while having a lesser effect on cardiorespiratory endurance (for example moderate-intensity activities).

Thus, both self-report of physical activity as measured by the 7-day PAR and the more precise measure of cardiorespiratory endurance, maximal oxygen consumption, will be coequal primary outcomes.

The need to maintain increases in physical activity to achieve health benefits has been documented, so the relatively long-term time frame of 24 months has been selected for the primary outcomes. In addition, the primary objectives will be addressed separately in the two genders because of some evidence that intervention effects may differ in men and women.

Two models of varying degrees of intervention are based on feasibility for delivery in a primary-care setting, behavioral principles previously shown to be effective, and the desire to provide options for intervention delivery.

Primary objectives are to determine:

- a. the effects in sedentary men and women of two primary-care based activity counseling regimens (B and C, representing the staff-assisted and staff-counseling interventions, respectively) on physical activity (defined as energy expenditure) ($\text{kcal}\cdot\text{kg}^{-1}\cdot\text{day}^{-1}$) after 24 months when compared to a Standard Care control (Group A) and to each other; and
- b. the effects in sedentary men and women of the two primary-care based activity counseling regimens (B and C) on cardiorespiratory endurance (defined as maximum oxygen consumption or $\text{VO}_{2\text{max}}$) ($\text{L}\cdot\text{min}^{-1}$) after 24 months when compared to Standard Care control and to each other.

2. Secondary Objectives

Although the primary purpose of ACT is to increase physical activity and cardiorespiratory endurance, a variety of secondary outcomes are important for assessing the effects of the interventions. These include short-term intervention effects, alternate measures of physical activity and fitness, levels of factors related to cardiovascular disease risk, psychosocial factors, and cost-effectiveness. These outcomes may be important for medical care practices to assess their relative enthusiasm for implementing physical activity intervention programs for their patients. In addition, intervention effects in different types of participants are important to assess. The interventions may be successful in some groups but not in others for a variety of reasons such as different perceptions, needs, abilities, or cultural factors.

Secondary objectives are to compare the relative effectiveness of the two primary-care based counseling regimens (Interventions B and C) to each other and vs. Standard Care (Group A) control on:

- a. the effects on physical activity and cardiorespiratory endurance after 6 months;
- b. the effects on submaximal treadmill test performance and shifts from sedentary to light and moderate activity after 6 and 24 months;
- c. the effects on factors related to cardiovascular disease risk (HDL-cholesterol, LDL-cholesterol, total cholesterol, triglycerides, blood pressure, plasma insulin, fibrinogen, body composition, dietary fat intake, smoking status, and heart rate variability) after 6 and 24 months;
- d. the effects on psychosocial factors (mood, self-efficacy, quality of life) after 6 and 24 months;
- e. the relative cost-effectiveness of the two regimens after 24 months;
- f. the effects after 6 and 24 months by subgroups categorized by the following factors:
 - age
 - ethnicity
 - body mass index
 - medication use (beta blockers or calcium channel blockers)

- smoking status
 - psychosocial variables (mood, self-efficacy, social support); and
- g. the relationship between adherence to the intervention protocols across the initial 6 month and overall 2 year periods and changes in cardiorespiratory fitness, physiological outcomes of interest, and quality of life outcomes.

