2. TRIAL DESIGN AND METHODS

2.A. Study Design

ACT is a multicenter, randomized controlled trial designed to test the effects of two primary-care practice-based physical activity interventions on the adoption and maintenance of physical activity in sedentary participants. The two interventions (B and C) will be compared to a Standard Care control group (Group A) and to each other. The primary outcomes of physical activity ($\text{kcal} \cdot \text{kg}^{-1} \cdot \text{day}^{-1}$) and VO_2max ($\text{L} \cdot \text{min}^{-1}$) will be analyzed separately for men and women. Participants will be randomly allocated and stratified by gender, race, and clinical site.

Eight hundred ten participants from three clinical centers (CCs) will each be randomly assigned to one of three study groups: A- Standard Care Control; B- Staff-Assistance Intervention; C- Staff-Counseling Intervention. In all three conditions, participants will receive physician advice to increase their physical activity and will be provided with current recommendations for physical activity (the CDC/ACSM recommendation of accumulating 30 minutes of moderate physical activity on most days of the week and the ACSM prescription for cardiorespiratory endurance). In Interventions B and C, behavior-change programs will be implemented that have been designed to help participants increase their physical activity in order to meet the recommendations. The major difference between these two interventions is the degree of resources and staff burden required. The interventions will be delivered by health educators throughout the two-year intervention period.

2.B. Study Population

Inclusion Criteria

The study population for ACT will consist of participants who are:

- community-dwelling men and women;
- 35-75 years of age;
- receiving primary care from a participating study physician;
- scheduled to see a study physician during the recruitment phase of the study;
- exhibiting a sedentary lifestyle, defined as energy expenditure of $\leq 35 \text{ kcal} \cdot \text{kg}^{-1} \cdot \text{day}^{-1}$ measured by 7-day PAR;
- willing and able to participate in all aspects of the trial;
- in stable health;
- independent in activities of daily living;
- able to alter physical activity in accordance with the intervention program;
- if on medication for chronic disease, on a stable dose for the last 3 months; and
- willing and able to give informed consent.

Exclusion Criteria

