Important secondary outcome measures include other measures of fitness and activity, factors related to cardiovascular risk (e.g. levels of lipoproteins, blood pressure, insulin, glucose, and fibrinogen), health related quality of life and cost. Methods similar to those described above will be used for continuous measures. For other types of response variables (categorical, ordered categorical, or counts), we will use the generalized estimating equation (GEE) approach to fit logistic or log-linear models that account for the dependency between repeated measures (Zeger and Liang, 1986; Liang and Zeger, 1986; Prentice, 1988; Zeger, 1988; Lipsitz, 1991; Liang, Zeger and Qaqish, 1992; Miller, 1993). Nonparametric approaches may also be adopted in some settings, as well (e.g. Zerbe and Walker, 1977; Raz, 1988).

A full description of compliance, predictors of compliance, and attrition comprise important

secondary analyses that will allow a more complete understanding of study results. Other important secondary analyses include descriptions of the effectiveness of interventions in pre-defined subgroups formed by race, age, and baseline measures of activity or fitness, body mass index, education, use of beta blockers, pre-existing co-morbid conditions, elevated ST segments, mood disorders, smoking, psychosocial factors and menopausal status. In some secondary analyses, data from women and men may be combined. Cross-sectional and longitudinal relationships among individual outcome measures, and between measures of adherence and outcomes, will also be described.

Importantly, the cross-sectional and longitudinal relationships between VO₂max and other measures of treadmill exercise performance and seven-day physical activity recall will be examined for internal consistency. The robustness of these relationships across study groups and participant subgroups will be assessed using regression analyses.

5.C. Sample Size Considerations

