Sample size calculations for the ACT trial were based on recruitment of an equal number of participants to each of its three groups. The two primary outcomes in these calculations are logarithmic-transformed VO₂max measurements (unadjusted for weight) and total kilocalorie expenditure per kilogram body weight by seven-day physical activity recall, including light, moderate and heavy activities, but not including sleep. For each primary outcome, the hypotheses to be tested will investigate 24-month differences between all intervention groups; thus a total of six pairwise comparisons will be performed. Preliminary data used for estimating standard deviations of outcomes were obtained from the SSHIP-I trial run by investigators at Stanford University. Based on the SSHIP-I information, we estimated that the standard deviations of log transformed, 24-month VO₂max measurements adjusted for baseline measurements were 0.1214 for men and 0.1215 for women, respectively. Standard deviations for total kilocalorie expenditure were only available for 12 months of follow-up. The 12-month standard deviations of total kilocalorie expenditure were 2.0894 for men and 2.0206 for women, after adjustment for baseline measurements. Sample size calculations were performed separately for men and women.

To ensure an overall, two-sided, Type I error rate, α , of 0.05, each pairwise comparison will be performed at the 0.0083 level (0.05/6), thus using critical regions containing 0.00417 probability in each tail. Assuming equal variances of 24-month outcomes for all intervention groups, the general formula used to determine the appropriate sample size to detect a difference of δ with $1-\beta$ power is

$$N = \left(\frac{1}{r} \right) V \left(\frac{1}{P_1} + \frac{1}{P_2} \right) \frac{(Z_{1-\alpha/2/m} + Z_{1-\beta})^2}{\delta^2},$$

where r is the proportion of participants that will not be lost to follow-up prior to 24 months, V is the baseline adjusted variance of the outcome variable, P_1 and P_2 are the proportion of subjects in the groups being compared, m is the number of trial groups times the number of primary outcomes, and $Z_{1-\alpha/2/m}$ and $Z_{1-\beta}$ are percentiles from a standard normal distribution. For the calculations reported below, we assume 20% loss to follow-up ($r = 0.8$) and have allowed equal numbers in each group. $Z_{1-\alpha/2/6} = Z_{0.00417} = 2.64$ and, for 90% power, $Z_{1-0.1} = 1.282$.

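### Effect modification by age, BMI, psychosocial scores and baseline activity or fitness is planned through categorised subgroups, with no treatment-by-continuous-baseline term; adding one is a cheap gain for secondary objective f

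*Protocol*

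**What the plan says.** Protocol section 1.B, Secondary Objectives, item f, sets out to compare the groups on "the effects after 6 and 24 months by subgroups categorized by the following factors". The list has six entries: age, ethnicity, body mass index, use of beta blockers or calcium channel blockers, smoking status, and psychosocial variables (mood, self-efficacy, social support).

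Section 5.B returns to this as a secondary analysis: "descriptions of the effectiveness of interventions in pre-defined subgroups formed by race, age, and baseline measures of activity or fitness, body mass index, education", followed by further factors including mood disorders, smoking and psychosocial factors. Baseline activity and fitness appear here and not in item f. The next sentence reads "In some secondary analyses, data from women and men may be combined".

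The one regression across subgroups mentioned in 5.B is "The robustness of these relationships across study groups and participant subgroups will be assessed using regression analyses". It concerns the relation of VO2max and other treadmill measures to the seven-day recall. It does not concern the treatment effect.

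The protocol states no cut-points, number of categories, interaction test or continuous modifier term for objective f.

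**The concern.** Objective f asks in which kinds of participant the interventions work. Ethnicity, medication use and smoking status are naturally categorical. Age, body mass index, the psychosocial scores, baseline seven-day recall and baseline VO2max are measured on a scale. The protocol describes all of them through subgroups. For the scaled measures, cutting treats everyone within a category as alike, so the gradient of effect inside each category is lost and the answer depends partly on where the cut falls.

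The protocol gives a reason to look separately by sex and by race/ethnicity (section 2.B, Inclusion of Women and Minorities). It gives none for cutting the scaled measures. At stake is how precisely a stated secondary objective is answered, using data already collected.

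**Working it through.** **1. The plan's own figures.** Section 5.C gives N = (1/r) · V · (1/P1 + 1/P2) · (z_α + z_β)² / δ². The inputs are r = 0.8, P1 = P2 = 1/3, z_α = 2.64, z_β = 1.282, δ = 1.1 kcal/kg/day and baseline-adjusted SDs of 2.0894 (men) and 2.0206 (women).

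- Men: 1.25 × 2.0894² × 6 × 3.922² / 1.21 = 416.2, against 417 stated.
- Women: 1.25 × 2.0206² × 6 × 3.922² / 1.21 = 389.3, against 393 stated.

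The sample size reproduces closely. It is set for pairwise group differences within each sex. No figure is stated for effect modification.

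**2. Information kept after categorising.** Assume the treatment effect changes linearly with the modifier. The share of information on the interaction that survives is the squared correlation between the modifier and its category means.

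- Normal modifier, median split: 2/π = 0.637.
- Normal modifier, k equal groups: the mean of the squared category means of a standard normal, which is 0.793, 0.861 and 0.897 for k = 3, 4 and 5.
- Normal modifier, two groups with a fraction p below cut c: φ(c)² / [p(1 − p)]. At p = 0.20 this is 0.280² / 0.16 = 0.490.
- Uniform modifier, k equal groups: 1 − 1/k².

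**3. Effect on power.** Take an interaction that would have 80% power in continuous form at two-sided 0.05, so its standardised size is 1.960 + 0.842 = 2.802. After categorising, power = Φ(2.802 × √kept − 1.960).

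| Modifier and grouping | Information lost | Power (from 80%) |
|---|---|---|
| Normal, median split | 36% | 61% |
| Normal, tertiles, ordered trend | 21% | 70% |
| Normal, quartiles, ordered trend | 14% | 74% |
| Normal, quintiles, ordered trend | 10% | 76% |
| Normal, 20/80 split | 51% | 50% |
| Uniform, halves | 25% | 68% |
| Uniform, tertiles, ordered trend | 11% | 75% |
| Uniform, quintiles, ordered trend | 4% | 78% |

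The finer groupings do this well only if an ordered trend is tested. If the groups are compared as unordered categories (noncentral chi-square on k − 1 degrees of freedom, noncentrality 2.802² × kept), power for a normal modifier is about 60%, 57% and 54% for tertiles, quartiles and quintiles. For a uniform modifier it is about 65% for tertiles and 58% for quintiles. The protocol does not say which comparison would be used.

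**4. What a two-group description would show.** Within one sex, 417 × 0.8 / 3 = 111.2 men and 393 × 0.8 / 3 = 104.8 women per group are expected at 24 months, so a median split leaves about 56 and 52 per group per half. The SDs in 5.C are 12-month values, used here as the protocol uses them.

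- Half-width of the 95% interval for a pairwise difference in one half, men: 1.96 × 2.0894 × √(2/55.6) = 0.78 kcal/kg/day. Women: 1.96 × 2.0206 × √(2/52.4) = 0.77.
- Half-width for the difference between halves: √2 times as wide, 1.10 (men) and 1.09 (women), about as large as the 1.1 effect that the trial is sized to detect.

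Pooling the sexes, where 5.B allows it, narrows these by about √2, but does not recover what the cut itself loses.

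**The case against.** The strongest objection is that the protocol names factors of interest and does not fix a model. It gives no cut-point, number of groups or test, and such details are commonly left to a statistical analysis plan, which is not shown here. This stands in part. Continuous modelling is not excluded, and missing cut-points are not a fault. But both sections describe the approach as subgroups, so a plan that followed them would supply cuts and would have no prompt to add a gradient.

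A reader might infer that the plan discards about a third of the information, or loses 17 to 19 points of power. The documents do not support that. Those figures need a near-median split of a roughly normal modifier, and the protocol specifies neither. Some ordinary schemes lose little: normal quintiles or uniform tertiles with a trend test cost less than 5 points of power from 80%. Normality is also doubtful for age, restricted by eligibility to "35-75 years of age", and for baseline seven-day recall, capped at 35 kcal/kg/day.

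A reader might also infer that these analyses are confined to sex-split samples, or that the trial would miss gradients that its data could detect. Section 5.B permits pooling in some secondary analyses, and nothing shows that any interaction would reach 80% power even in continuous form; the 80% in the working is only a reference point. The cuts are to be pre-defined, which guards against choosing them from the data, though not against an arbitrary prior choice.

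Finally, the planned analyses are secondary and descriptive, and subgroup effects do answer a question about groups. That limits the weight of the point and is a good reason to keep the categories for display.

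**Conclusion.** The point holds as a modest improvement. For modifiers measured on a scale, the protocol describes categorised subgroups and plans no treatment-by-continuous-baseline term. If the gradient is roughly linear, categorising loses information on objective f. The loss cannot be fixed at one number: among the schemes worked through it runs from about 4% (uniform quintiles with a trend) to about 51% (20/80 split of a normal modifier), with about 36% for a normal median split. These figures rest on linearity and on an assumed distribution and grouping, since the protocol gives none of these. Where the gradient is a sharp step, a well-placed category could do as well or better.

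**What to change.** In section 5.B, add that effect modification by age, body mass index, baseline seven-day recall, baseline VO2max, mood, self-efficacy and social support will be estimated with a treatment-by-continuous-baseline-value term in the 6- and 24-month models. Present predicted group differences at representative values of each factor, check linearity (for example with a quadratic term), and pool the sexes where 5.B allows. Keep the pre-defined categories for descriptive display and for the truly categorical factors: race/ethnicity, smoking and medication use.

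The cost is a few lines of analysis text and one extra interaction term per factor, with the factor's own main effect where the model does not already hold it. The downside is the linearity assumption, which the quadratic term can check. No new data, visits or participants are needed.
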